Patients must only be identified by the subject identification ID (Center number, Patient number

Adverse Event Log/Concomitant Medication Log

If additional pages of adverse event and / or concomitant medication log are required, please make a photocopy of a blank adverse Event log / concomitant medication log and complete the information. The original page will be sent to data management and a photocopy retained at Minapharm and investigator site

Dates

- 1- All dates are to be reported in the format DD/MMM/YYYY
- 2- The month is to be reported as the first three characters of the month, e.g. 01/AUG/2012 the month abbreviations are as follows:

January	=	Jan	May	=	May	September	=	Sep
February	=	Feb	June	=	Jun	October	=	Oct
March	=	Mar	July	=	Jul	November	=	Nov
April	=	Apr	August	=	Aug	December	=	Dec

3- In the absence of a precise date for an event or therapy that precedes the participant's inclusion into the study, a partial date may be recorded by recording "NK" in the fields that are unknown e.g. where the day and month are not clear, the following may be entered into the CRF:

0	0	Μ	A	R	2	0	0	9
DD MN		1MI	M		YY	ΥY		

Center Numbering:

Enter the center number (2 digits),

- Research Center of Air Force Specialized Hospital = 01
- Helwan University Hospital = 02

e.g.

Center Nº:	0	1
------------	---	---

Patient's	Patient's	Screening Visit
Nº:	Initials:	Initiation Visit

[figure not shown]
Patients' Numbering;

Enter Patients' Group (A, B, or C), then patient's number (from 001 to 297), e.g.

Patient's Nº	А	0	0	5	
--------------	---	---	---	---	--

No Carbon Required (NCR) CRF

The White original and the pink NCR CRF Will be retrieved by Minapharm personnel during his / her visit to the center. The yellow NCR card will be retained by investigator folder at the site

A study population of 297 patients with compensated chronic Liver Disease, will be randomized according to fibroscan in screening visit into 2 groups:

- Group 1: with non-cirrhosis, F0, F1 and F2.
- Group 2: with advanced fibrosis and cirrhosis, F3 and F4

Subjects will be randomized into the 3 treatment groups with a balanced ratio of 1:1:1

- Group A (Experimental group), will receive Ursoplus[®] capsules (UDCA 250mg & Silymarin 140mg) = 99 subjects
- Group B (Control group 1), will receive Ursofalk[®] capsules (UDCA 250mg) = 99 subjects
- Group C (Control group 2), will receive Placebo = 99 subjects

Patient's		
Initials:		

[figure not shown]
Child-Pugh Score Calculation:

The score employs five clinical measures of liver disease. Each measure is scored 1-3, with 3 indicating most severe derangement.

Measure	1 point	2 points	3 points
Total bilirubin, µmol/l (mg/dl)	<34 (<2)	34-50 (2-3)	>50 (>3)
Serum albumin, g/dl	>3.5	2.8-3.5	<2.8
Prothrombin time prolongation (secs)	<4.0	4.0-6.0	> 6.0
Ascites	None	Mild	Moderate to Severe
Hepatic encephalopathy	None	Grade I-II (or suppressed with medication)	Grade III-IV (or refractory)

In primary sclerosing cholangitis (PSC) and primary biliary cirrhosis (PBC), the bilirubin references are changed to reflect the fact that these diseases feature high conjugated bilirubin levels. The upper limit for 1 point is 68 μmol/l (4 mg/dl) and the upper limit for 2 points is 170 μmol/l (10 mg/dl).

Chronic liver disease is classified into Child-Pugh class A to C, employing the added score from above.

Patient's		Patient's	Screening Visit
Nº:		Initials:	Initiation Visit

Screening Visit

Date of Screening: ___/ ___ (DD / MMM / YYYY)

Informed Consent:

Date patient signed

written consent form:

___/___/_____

(DD / MMM / YYYY)

Inclusion/ Exclusion Criteria

	Inclusion Criteria	N	Na
	ollowing criteria MUST be answered YES for participant to be led in the trial:	Yes	No
1.	Male or female patient aged ≥ 18		
2.	Subjects with Compensated Chronic Liver Disease, defined as child 5-7.		
3.	Patients with mild disturbance of liver biochemical profile (Elevated Total Serum Bilirubin \leq 3 mg/dl, or elevated Direct Serum Bilirubin \leq 2 mg/dl, or elevated one or more of liver enzymes up to 3 times of the normal level (Alanine Transaminase (ALT), Aspartate Aminotransferase (AST), Alkaline Phosphatase (ALP) & Gamma Glutamyl Transpeptidase (GGT)).		
4.	Non-diabetic subjects and subjects with Co ntrolled DM-type 1 and 2 patients, HbA1C up to 7.5%		
5.	Non-pregnant or lactating female patients		
6.	Subjects who are willing to sign Informed Consent Form and ready to comply with the protocol for the duration of the study		

	Exclusion Criteria	Nee	Na
	following criteria MUST be answered NO for participant to be uded in the trial:	Yes	No
1.	Subjects with a history of hypersensitivity to any of the ingredients of the medication being studied		
2.	Subjects with positive PCR in the past 6 months		
3.	Subjects with positive Hepatitis B surface antigen (HBsAg)		

Pa	atien	ıť	s
N٥	:		

Patient's	
Initials:	

Screening Visit Initiation Visit

4.	Subjects with elevated liver enzymes more than 3 times of the normal level (Alanine Transaminase (ALT), Aspartate Aminotransferase (AST), Alkaline Phosphatase (ALP) & Gamma Glutamyl Transpeptidase (GGT)).	
5	Subjects with Primary Biliary Cirrhosis (PBC) and Primary Sclerosing Cholangitis (PSC)	
6	Subjects with Child Pugh Score more than 7	
7	Subjects with history of bleeding varices	
8.	Subjects having uncontrolled Diabetes (HbA1c above 7.5 %)	
9.	 Subjects with any medical condition require the usage of medication may interfere with the absorption, distribution, metabolism or excretion of the drugs such as: 1- Bile acid sequestering agents such as cholestyramine and colestipol, 2- Antacids containing aluminum hydroxide. 3- Drugs affecting lipid metabolism such as estrogens, oral and hormonal contraceptives, and clofibrate (and perhaps other lipid-lowering drugs) 	
10.	Subjects who are receiving other liver support drugs (including drugs of the study), 1 month before study initiation.	
11	Subjects with auto immune liver disease taking corticosteroid or immune suppressant	
12.	Pregnant or breast-feeding women	
13	Use of oral contraceptives in child bearing ladies	

Demographic Data & Vital Signs

Patient Demography & Vital Signs:								
Gender:	Male	Female						
Birthdate:	//		(DD / MMM / YYYY)					
Weight:	Kg		Height:	cm				
Blood Pres	sure (Systolic/Di	astolic):	/	_mmHg				

Patient's		Patient's		Screening Visit
Nº:		Initials:		Initiation Visit

Habits					
Smoking Habits:					
Does the subject smoke or use tobacco products?	🗌 Yes	🗌 No			
How many cigarettes per day?					
Others, specify:					

☐ Yes	🗌 No
	☐ Yes

Physical Examination

*Please fill the relevant forms of adverse events in case any abnormal or untoward event is noticed

Physical Examination	Normal	Abnormal	
Findings		 	

Medical History

Has the patient had any relevant medical history?	🗌 No	Yes, Complete below
---	------	----------------------------

Patient's Nº:		Patient's Initials:	Screening Visit Initiation Visit

Condition / illness /surgical procedure	Start date (DD/MMM/YYYY)	Stop date (DD/MMM/YYYY)	Or tick if ongoing ?	
	//	//		
	//	//		
	//	//		

Is the participant taking any concomitant medications?	No Yes If Yes: Complete Concomitant Medication Page 26				
Abdominal Ultrasound					

Date of Ultrasound: ____/ ___/ (DD / MMM / YYYY)

Liver	Normal		Abnormal			
If abnormal, findings:	Portal Vein Diameter:mm (N. up to 14mm)					
	Ascites:	No Yes	If yes, Amount: .			
Spleen	Normal		Abnormal			
lf abnormal,						
findings:	Splenic Vein Diameter:mm					
Gall Bladder	Normal		Abnormal			
lf abnormal,						
findings:	Common B	ile Duct (CBD) Diame	ter:mm (Ν. ι	ıp to 6mm)		

Patient's		Patient's	Screening Visit
Nº:		Initials:	Initiation Visit

Vibration-controlled transient elastography with CAP (Fibroscan)

Date of Fibroscan: ___/ ___/ (DD / MMM / YYYY)

	Liver stiffness measurement	Fi	broscan score	
Liver		F0/F1	F2	
		F3	F4	
If abnormal, findings:				
Safety Laboratory Tests				

Date of Laboratory Tests: __/ __/ (DD / MMM / YYYY)

Laboratory Parameter	Value	Unit	If parameter indicated as out of normal range on report, please check if clinically significant:
ALT			🗌 No 🔄 Yes
AST			□ No □ Yes
Alkaline Phosphatase (ALP)			□ No □ Yes
Gamma-GT			□ No □ Yes
Total Bilirubin			□ No □ Yes
Direct bilirubin			□ No □ Yes
S Albumin			□ No □ Yes
РТ			□ No □ Yes
HbA1c for diabetic patients			□ No □ Yes
PCR/ Antibody for hepatitis C			□ No □ Yes
HBs Ag			□ No □ Yes
Serum β -HCG (for Females in child bearing period)			□ No □ Yes

Patient's		Patient's		Screening Visit
Nº:		Initials:		Initiation Visit

Assessment for quality of life (The RAND 36-Item Health Survey)

Completed

Not Completed

End of Screening Visit

End	of Screening Visit Checklist:	Yes	No
1.	Does the participant meet the inclusion and exclusion criteria to date?		
2.	Have all Screening Visit procedures been completed?		
3.	Have the Medical History and Concomitant Medication pages been completed?		

Participant's eligibility:
Is the participant eligible to take part in the Clinical Study?
☐ Yes
□ No, Please give reason for screen failure below
Reason(s) for screen failure:
1.
2.
Investigator Sign-Off
Investigator's Name:
Investigator's Signature: Date ://
(DD / MMM / YYYY)

Patient's Nº:		Patient's Initials:		Scre Initi	ening Visit ation Visit		
	Randomization						
Group A	A	Group B		Group C			
			·				
Drug Dispense							

Date of Drug Dispense: ___/ ___ (DD / MMM / YYYY)

Drugs are dispensed for the patient to be sufficient for 30 days of treatment The subject is asked to take the treatment daily and come next visit with the empty blisters after 30 days, with a window of 7 days.

Drug Dispense	Number of Capsules	Number of Blisters
Drug A, B, or C		

Investigator's Name:

Investigator's Signature: _____ Date: ___/ ___/

(DD / MMM / YYYY)

Visit 2 (Week 4) (may be done by phone call)

Date of Visit 2: ___/ ___ (DD / MMM / YYYY)

Vital Signs

Vital Signs & Weight:

Weight: _____ Kg

Blood Pressure (Systolic/Diastolic): ____ / ___ mmHg

Physical Examination

*Please fill the relevant forms of adverse events in case any untoward or unusual event that occurred since last visit, whether it is believed to be related to the study drug or not.

Physical Examination	Normal	Abnormal	
Findings		 	
Findings		 	

Drug Dispense

Date of Drug Dispense: ___/ ___ (DD / MMM / YYYY)

Drug Dispense	Number of Capsules	Number of Blisters
Drug A, B, or C		

Patient's Nº:	Patient's Initials:		Visit 2 (Week 4) Follow Up Visit 1
------------------	------------------------	--	--

Drugs are dispensed for the patient to be sufficient for 30 days of treatment The subject is asked to take the treatment daily and come next visit with the empty blisters after 30 days, with a window of 7 days.

Is the participant taking any concomitant medications?	No Yes If Yes: Complete Concomitant Medication
conconntant medications ?	Page 26

Is the participant had any Adverse Events

The investigator shall ask probing questions, allowing the patient to tell about any untoward or unusual event that occurred since the last visit, whether he/she (the patient) believes it is related to the study drug or not? (including abnormal physical examination/ laboratory results)	☐ No ☐ Yes If Yes: Complete Page 30
---	---

I have updated the AEs on page And have assessed them for seriousness, causality, severity and outcome and confirm that, to the best of my knowledge, it accurately reflects the study information obtained for this participant:

Investigator's Name: _____

Investigator's Signature: _____ Date: ___/ ___/

(DD / MMM / YYYY)

Patient's	
Nº:	

Visit 3 (Week 8) (may be done by phone call)

Date of Visit 3: ___/ ___ (DD / MMM / YYYY)

Vital Signs

Vital Signs & Weight:

Weight: _____ Kg

Blood Pressure (Systolic/Diastolic): ____ / ___ mmHg

Physical Examination

*Please fill the relevant forms of adverse events in case any untoward or unusual event that occurred since last visit, whether it is believed to be related to the study drug or not.

Physical Examination	Normal	Abnormal	
Findings		 	

Drug Dispense

Date of Drug Dispense: ___/ ___ (DD / MMM / YYYY)

Drug Dispense	Number of Capsules	Number of Blisters
Drug A, B, or C		

Patient's
Nº:

Drugs are dispensed for the patient to be sufficient for 30 days of treatment The subject is asked to take the treatment daily and come next visit with the empty blisters after 30 days, with a window of 7 days.

Is the participant taking any concomitant medications?	No Yes If Yes: Complete Concomitant Medication
	Page 26

Is the participant had any Adverse Events

I have updated the AEs on page And have assessed them for seriousness, causality, severity and outcome and confirm that, to the best of my knowledge, it accurately reflects the study information obtained for this participant:

Investigator's Name:

Investigator's Signature: _____ Date: ___/ ___/

(DD / MMM / YYYY)

Patient's Nº:		Patient' s Initials:			Visit 4 (Week 12) Follow Up Visit 3
		initiais:			•

Visit 4 (Week 12)

Date of Visit 4: ___/ ___/ (DD / MMM / YYYY)

Vital Signs

Vital Signs & Weight:

Weight: _____ Kg

Blood Pressure (Systolic/Diastolic): ____ / ___ mmHg

Physical Examination

*Please fill the relevant forms of adverse events in case any untoward or unusual event that occurred since last visit, whether it is believed to be related to the study drug or not.

Physical Examination	Normal	Abnormal	
Findings			

The RAND 36-Item Health Survey				
Completed		Not Completed		

Patient's Nº:		Patient' s		Visit 4 (Week 12) Follow Up Visit 3
		Initials:		

Drug Dispense

 Date of Drug Dispense:
 /
 /
 (DD / MMM / YYYY)

Drug Dispense	Number of Capsules	Number of Blisters
Drug A, B, or C		

Drugs are dispensed for the patient to be sufficient for 30 days of treatment The subject is asked to take the treatment daily and come next visit with the empty blisters after 30 days, with a window of 7 days.

Is the participant taking any	🗌 No 🔄 Yes		
concomitant medications?	If Yes: Complete Concomitant Medication		
	Page 26		

Is the participant had any Adverse Events

I have updated the AEs on page And have assessed them for seriousness, causality, severity and outcome and confirm that, to the best of my knowledge, it accurately reflects the study information obtained for this participant:

Investigator's Name: _____

Investigator's Signature: _____ Date: ___/ ___/

(DD / MMM / YYYY)

Patient' s Initials:

als:

Visit 5 (Week 16) (may be done by phone call)

Date of Visit 5: ___/ ___ (DD / MMM / YYYY)

Vital Signs

Vital Signs & Weight:

Weight: ____ Kg

Blood Pressure (Systolic/Diastolic): _____ / ____ mmHg

Physical Examination

[figure not shown]
*Please fill the relevant forms of adverse events in case any untoward or unusual event that occurred since last visit, whether it is believed to be related to the study drug or not.

Physical Examination	Normal	Abnormal	
Findings		 	

Drug Dispense

Date of Drug Dispense: ___/ ___ / ___ (DD / MMM / YYYY)

Drug Dispense	Number of Capsules	Number of Blisters
Drug A, B, or C		

Drugs are dispensed for the patient to be sufficient for 30 days of treatment The subject is asked to take the treatment daily and come next visit with the empty blisters after 30 days, with a window of 7 days.

Is the participant taking any	🗌 No 🔄 Yes		
concomitant medications?	If Yes: Complete Concomitant Medication		
conconntant medications :	Page 26		

Is the participant had any Adverse Events

The investigator shall ask probing questions, allowing the patient to tell about any untoward or unusual event that occurred since the last visit, whether he/she (the patient) believes it is related to the study drug or not? (including abnormal physical examination/ laboratory results)	No ☐ Yes If Yes: Complete Page 30
---	---

I have updated the AEs on page And have assessed them for seriousness, causality, severity and outcome and confirm that, to the best of my knowledge, it accurately reflects the study information obtained for this participant:

Investigator's Name: _____

Investigator's Signature: _____ Date: ___/ ___/

(DD / MMM / YYYY)

Patient' S Initials:

Visit 6 (Week 20) (may be done by phone call)

Date of Visit 6: ___/ ___ (DD / MMM / YYYY)

Vital Signs

Vital Signs & Weight:

Weight: ____ Kg

Blood Pressure (Systolic/Diastolic): ____ / ___ mmHg

Physical Examination

[figure not shown]
*Please fill the relevant forms of adverse events in case any untoward or unusual event that occurred since last visit, whether it is believed to be related to the study drug or not.

Physical Examination	Normal	Abnormal	
Findings		 	

Drug Dispense

Date of Drug Dispense: ___/ ___ / ___ (DD / MMM / YYYY)

Drug Dispense	Number of Capsules	Number of Blisters
Drug A, B, or C		

Drugs are dispensed for the patient to be sufficient for 30 days of treatment The subject is asked to take the treatment daily and come next visit with the empty blisters after 30 days, with a window of 7 days.

Is the participant taking any	🗌 No 🔄 Yes		
concomitant medications?	If Yes: Complete Concomitant Medication		
concomitant medications?	Page 26		

Is the participant had any Adverse Events

I have updated the AEs on page And have assessed them for seriousness, causality, severity and outcome and confirm that, to the best of my knowledge, it accurately reflects the study information obtained for this participant:

Investigator's Name:

Investigator's Signature: _____ Date: ___/ ___/ ____ [DD / MMM / YYYY]

Patient's Nº:		ient's tials:			End of Study Visit (Week 24)
	End	of study			
Date of End of study visit: _	111	(DE) / MMM / YYY	Y)	
	Vita	al Signs			
Vital Signs & Weight:					
Weight: Kg					
Blood Pressure (Systolic/D	viastolic):	/	mn	nHg	
	Physical	l Examina	ation		
*Please fill the relevant forms since last visit, whether it is be		•			ent that occurred
Physical Examination	Normal			Abnormal	

Physical Examination	Normal	Abnormal	
Findings		 	

The RAND 36-Item Health Survey					
Completed		Not Completed			

Patient's Nº:			Patient's			End of Study Visit
Fallents N.			Initials:			(Week 24)

Safety Laboratory Tests

Date of Laboratory Tests: ___/ ___ (DD / MMM / YYYY)

Laboratory Parameter	Value	Unit	If parameter indicated as out of normal range on report, please check if clinically significant:
ALT			🗌 No 🔄 Yes
AST			□ No □ Yes
Alkaline Phosphatse (ALP)			□ No □ Yes
Gamma-GT			□ No □ Yes
S.Albumin			□ No □ Yes
Total Bilirubin			□ No □ Yes
Direct bilirubin			□ No □ Yes
Serum β -HCG (for Females with child bearing potential only)			□ No □ Yes

Vibration-controlled transient elastography with CAP (Fibroscan)

Date of Fibroscan: ___/ ___ (DD / MMM / YYYY)

	Liver stiffness measurement	Fibroscan score		
		F0/F1		
Liver		☐ F2		
		F 3		
		☐ F4		
lf abnormal, findings:				

Is the participant taking any	□ No □ Yes
concomitant medications?	

Patient's Nº:		tient's tials:			End of Study Visit (Week 24)
		If Yes: Cor	mplete Cond	comita 26	nt Medication Page

Is the participant had any Adverse Events

The investigator shall ask probing questions, allowing the patient to tell about any untoward or unusual event that occurred since the last visit, whether he/she (the patient)	No Yes If Yes: Complete
believes it is related to the study drug or not? (including abnormal physical examination/ laboratory results)	Page 30

[figure not shown]
I have updated the AEs on page And have assessed them for seriousness, causality, severity and outcome and confirm that, to the best of my knowledge, it accurately reflects the study information obtained for this participant:

Investigator's Name:

Investigator's Signature: _____ Date: ___/ ___/

(DD / MMM / YYYY

[figure not shown]

Concomitant Medication Form

Medication (Record Generic or trade name)	Reason for use (Medical History diagnosis or other reason, e.g. Prophylaxis)	Dose and units	Frequency	Route	Start Date (DD/MMM/YYYY)	Stop Date (DD//MMM/YYY)	Or tick if ongoing
1.					//	I	
2.					//	//	
3.					//	//	
4.					/	/	
5.							
6.							
7.					I		
PI signature			·	Date: _	•	·	

CONFIDENTIAL

[figure not shown]
Patient's Nº:				
---------------	--	--	--	--

[figure not shown]

Adverse Events (1/2)

AE No	Event Name (Please give Diagnosis if known)	Start date (DD/MMM/YYYY)	Stop date (DD/MMM/YYYY)	Serious?	comitant Medication	Severity 0 - Mild 1- Mode- rate 2 - Severe	Study Drug Action 0 - None 1 - Temporarily Interrupted 2 - permanently withdrawn	Outcome 1- Death related to AE 2- Not resolved/Not recovered 3- Resolved/ Recovered 4- Resolved/ Recovered with Sequelae 5- Resolving/ Recovering 6- Unknown	Relationship to Study Drug 0 - Certain 1 – Probable/Likely 2 - Possible 3 - Unlikely 4 – Conditional/ Unclassified 5 - Un-assessable/ Unclassifiable
				🗌 No	🗌 No				
1		//	//	🗌 Yes	Yes				
				🗌 No	🗌 No				
2		//	//	🗌 Yes	Yes				
				🗌 No	🗌 No				
3		//	//	🗌 Yes	Yes				
				🗌 No	🗌 No				
4		//	//	🗌 Yes	Yes				
				🗌 No	🗌 No				
5		//	//	🗌 Yes	Yes				
	I have reviewed the A knowledge, it accurat					ısality, se∖	verity and ou	Itcome and confirm	that, to the best of my
	PI signature				Date:				

Patient's N°:

Adverse Events (2/2)

AE No	Event Name (Please give Diagnosis if known)	Start date (DD/MMM/YYYY)	Stop date (DD/MMM/YYYY)	Serious?	Con- comitant Medication given	Severity 0 - Mild 1- Mode- rate 2 - Severe	Study Drug Action 0 - None 1 - Temporarily Interrupted 2 - permanently withdrawn	Outcome 1- Death related to AE 2- Not resolved/Not recovered 3- Resolved/ Recovered 4- Resolved/ Recovered with Sequelae 5- Resolving/ Recovering 6- Unknown	Relationship to Study Drug 0 - Certain 1 – Probable/Likely 2 - Possible 3 - Unlikely 4 – Conditional/ Unclassified 5 - Un-assessable/ Unclassifiable
				🗌 No	🗌 No				
1		//	//	Yes	🗌 Yes				
				🗌 No	🗌 No				
2		//	//	C Yes	🗌 Yes				
				🗌 No	🗌 No				
3		//	//	🗌 Yes	🗌 Yes				
				🗌 No	🗌 No				
4		//	//	🗌 Yes	🗌 Yes				
				🗌 No	🗌 No				
5		//	//	🗌 Yes	🗌 Yes				
	I have reviewed the knowledge, it accura					usality, sev	verity and ou	tcome and confirm	hat, to the best of my
	PI signature				Date:				

Patient's Nº:		Patient's Initials:			Unscheduled Visit
				-	

Date of Unscheduled Visit: / /

____ (DD / MMM / YYYY)

Vital Signs

Vital Signs & Weight:

Weight: _____ Kg

Blood Pressure (Systolic/Diastolic): ____ / ___ mmHg

Physical Examination

*Please fill the relevant forms of adverse events in case any untoward or unusual event that occurred since last visit, whether it is believed to be related to the study drug or not.

Physical Examination	Normal	Abnormal	
Findings		 	

Is the participant taking any	No Yes		
concomitant medications?	If Yes: Complete Concomitant Medication		
conconnitant medications :	Page 26		

Is the participant had any Adverse Events

The investigator shall ask probing questions, allowing the patient to tell about any untoward or unusual event that occurred since the last visit, whether he/she (the patient) believes it is related to the study drug or not? (including abnormal physical examination/ laboratory results)		Complete 30
---	--	-------------

I have updated the AEs on page And have assessed them for seriousness, causality, severity and outcome and confirm that, to the best of my knowledge, it accurately reflects the study information obtained for this participant:

Investigator's Name:

Investigator's Signature: _____ Date: ____/ ____/

(DD / MMM / YYYY)	
-------------------	--

Patient's Nº:			Patient's Initials:			Study Completion page
Study Completion						
Did participant	complete	the trial?				
Yes, Please pro	ovide date of	f last day:				
/ / 2 0 (DD / MMM / YYYY)						
No, Please provide date of withdrawal and complete below:						
/	/20		(DD / I	MMM / YYY	Y)	
Early Withdrawa trial:	al: please	tick mos	t appropriate r	eason for p	particip	ant not completing the
Adverse Events related: please state related AE:(add details to AE page)						
Participant's decision, specify:						
☐ Investigator's decision, specify:						
Sponsor's decision						
□ Lost to follow up						
Patient deceased						
☐ Ineligibility (either arising during the study or retrospective having been overlooked at screening)						
Significant protocol deviation						
Significant non-compliance with treatment regimen or study requirements						
Disease progression which requires discontinuation of the study medication or results in inability to continue to comply with study procedures						
Consent with	hdrawn.					
Pregnancy or discontinuation of contraception						
Other, specify:						
Investigator Sig	jn off					
Investigator's N	lame:					
Investigator's S	ignature:				 D / MMM ;

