11.2 Analysis populations

Analysis of all efficacy variables will be performed only for patients who completed the study without protocol violation (as per protocol).

Analysis of all safety variables will be performed for all patients (intent-to-treat population) who received even 1 dose of the treatment; either Ursoplus[®] capsules or UDCA or Placebo.

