12.3.3 Safety Analysis

 Table 12
 Number and percent of Adverse Event among treatment groups

| | Group 1 | | | n valua | Group 2 | | | n value |
|--------------------------|---------|------|---------|-----------------|---------|------|---------|-----------------|
| | Urso | UDCA | Placebo | p -value | Urso | UDCA | Placebo | p -value |
| Total No of AE, N (%) | | | | | | | | |
| AE1, N (%) | | | | | | | | |
| AE2, N (%) | | | | | | | | |
| AE3, N (%) | | | | | | | | |
| | | | | | | | | |
| | | | | | | | | |

 Table 13
 Number and percent of Serious Adverse Event among treatment groups

| | Group 1 | | | - value | Group 2 | | | n volue |
|------------------|---------|------|---------|-----------------|---------|------|---------|-----------------|
| | Urso | UDCA | Placebo | p -value | Urso | UDCA | Placebo | p -value |
| Total SAE, N (%) | | | | | | | | |
| SAE1, N (%) | | | | | | | | |
| SAE2, N (%) | | | | | | | | |
| SAE3, N (%) | | | | | | | | |
| | | , | | | | | | |

> Concomitant Medication

 Table 14
 Number and percent of Concomitant medication among treatment groups

| | Group 1 | | | n valua | Group 2 | | | n value |
|----------------|---------|------|---------|-----------------|---------|------|---------|-----------------|
| | Urso | UDCA | Placebo | p -value | Urso | UDCA | Placebo | p -value |
| N | | | | | | | | |
| ConMed1, N (%) | | | | | | | | |
| ConMed2, N (%) | | | | | | | | |
| ConMed3, N (%) | | | | | | | | |
| | | | | | | | | |
| | | | | | | | | |

¹ - SF El Menshawe, AS Ahmed, LN Abdelaty, MA Aboseif. "Study of Hepatoprotective Effect of Silymarin and Ursodeoxycholic Acid in Chronic Hepatitis C Patients". Medicine Science 2014;3(4):1655-74

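### Abnormal findings noted at the screening examination go to the adverse event form, and the SAP has no onset rule to keep them out of the on-treatment AE counts

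*Protocol*

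**What the plan says.** The Protocol document is the case report form (CRF). Under Screening Visit, Physical Examination, it instructs: "Please fill the relevant forms of adverse events in case any abnormal or untoward event is noticed". The instruction has no time limit. In the order of the form, eligibility sign-off, randomisation and first dispensing ("Drugs are dispensed for the patient to be sufficient for 30 days of treatment") all come later.

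The same note on the follow-up examination pages is bounded in time: forms are to be filled "in case any untoward or unusual event that occurred since last visit".

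The population is defined by existing disease. Inclusion criterion 2 asks for a Child score of 5 to 7, and criterion 3 begins "Patients with mild disturbance of liver biochemical profile".

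On analysis, SAP section 11.2 states: "Analysis of all safety variables will be performed for all patients (intent-to-treat population) who received even 1 dose". That selects patients. Sections 5.2 and 11.4.2 list adverse and serious adverse events without an onset condition. Table 12 is titled "Number and percent of Adverse Event among treatment groups" and has a p-value column within each fibrosis group; Table 13 has the same layout for serious events. Neither document defines a treatment-emergent event.

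The CRF collects a start date for each adverse event and a date of first dispensing. A Medical History table with a tick box for ongoing conditions follows the screening examination.

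**The concern.** A finding noticed before any study drug has been handed out cannot be an effect of that drug. In compensated chronic liver disease, some abnormal examinations at entry are to be expected. If sites follow the screening note, those findings sit in the same log as on-treatment events. If the analyst follows the SAP, they are counted for every patient who later takes one dose.

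Because the entries are made before allocation, they should fall evenly on the arms. They would raise the reported AE percentage everywhere and pull the arms together. Safety of the combination against UDCA alone and against placebo is a secondary objective, so a comparison drawn towards no difference errs in the reassuring direction.

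**Working it through.** **Does the text lead there?**

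1. Recording: the screening note covers anything abnormal or untoward that is noticed, with no onset limit; the follow-up notes limit themselves to the interval since the last visit.
2. Order: the screening examination precedes randomisation and dispensing in the CRF, so what is noticed there is pre-dose.
3. Patient filter: SAP 11.2 requires one dose. A patient with a screening entry who is then dosed passes it.
4. Event filter: none appears in SAP 5.2, 11.2, 11.4.2 or Tables 12-13.

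A screening entry in a dosed patient is therefore counted if the plan is applied as written.

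**How large could it be?** The documents state no AE rate, so there is no figure of theirs to reproduce. Inputs:

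- p1, p2: true post-dose proportions with an AE. Assumed 20% and 10%, then 25% and 10%.
- b: share of patients with a screening entry on the AE form. Unknown; assumed from 10% to 60%, equal in all arms and independent of later events.

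Observed proportion in an arm = 1 - (1-b)(1-p).

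Observed difference = (1-b)(1-p2) - (1-b)(1-p1) = (1-b)(p1-p2).

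For example, at b = 30%: 1 - 0.7 × 0.8 = 44%, and 1 - 0.7 × 0.9 = 37%.

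| b | p1 = 20% shows as | p2 = 10% shows as | Difference | Risk ratio |
|---|---|---|---|---|
| 0 | 20% | 10% | 10 points | 2.00 |
| 10% | 28% | 19% | 9 points | 1.47 |
| 30% | 44% | 37% | 7 points | 1.19 |
| 60% | 68% | 64% | 4 points | 1.06 |

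With 25% against 10%, the 15-point difference becomes 13.5, 10.5 and 7.5 points at b = 10%, 30% and 50%, and the risk ratio falls from 2.50 to 1.71, 1.28 and 1.14. If there is no true difference, both rates rise and the difference stays at zero.

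**Power, as an illustration only.** Use the arcsine approximation, two-sided 5%: power ≈ Φ(h√(n/2) - 1.96), with h = 2 arcsin√p1 - 2 arcsin√p2 on the observed proportions. For 20% against 10% and n = 99 per arm, h = 0.284 and 0.284 × 7.036 - 1.96 ≈ 0.04, so power is about 0.51. At b = 10%, 30% and 60% it is 0.32, 0.17 and 0.09. The SAP tables are split by fibrosis group, however. With an assumed even split of about 50 per arm, power starts at 0.29 and falls to 0.11 at b = 30%.

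**The case against.** The strongest reply is that inflation is possible but not certain. The screening note speaks of an event, and directly beneath it is a space for examination findings, followed by Medical History. The screening pages carry no AE question, and the end-of-screening checklist asks for the Medical History and Concomitant Medication pages, not the AE log. A sensible site could record pre-existing signs without using the AE form. SAP 11.3 also foresees a final SAP before database lock, which could add an onset rule. All of this stands. It makes b unknown and possibly small, but it does not supply the missing rule.

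The reach is also limited. An individual AE row is diluted only where the screening entry uses the same term. If the total row of Table 12 counts events rather than patients, the formula above does not apply: equal extra entries would leave the difference in mean counts unchanged and pull only the ratio towards 1. The pooled comparison at 99 per arm is not what the tables present, and the within-group comparisons are weak even without contamination, so the power figures should not be read as the loss in this trial.

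A reader might go further and infer that liver tests still raised at follow-up will be logged as adverse events, so that an arm that normalises fewer patients looks less safe. The documents do not support this. The words "including abnormal physical examination/ laboratory results" sit inside a question limited to untoward or unusual events since the last visit. SAP 5.2 and 11.4.2 refer to changes in laboratory tests, which implies comparison with an earlier value. After screening, laboratory tests appear only on the End of Study page, with a clinical-significance box. A persistently raised entry value is not naturally such an event.

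**Conclusion.** The gap is real and lies in the combination of two texts: a screening note that routes abnormal findings to the AE form with no time limit, and a SAP that filters patients by dosing but never filters events by onset. Pre-existing signs may be counted as AEs in every arm, mainly in the total row of Table 12.

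The shrinkage factor (1-b) follows algebraically if the entries are independent of arm and of later events and the row counts patients. The points lost depend on assumed rates and an unknown b, so the figures show a range and do not forecast the result. Two stronger readings a reader might draw are not supported: that inflation is bound to occur, since sites have another place to record such findings; and that the serious-event table is equally exposed, since a screening finding must first be marked serious. The bias expected is towards no difference, because the screening examination precedes randomisation even though the study is open label.

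**What to change.** In SAP 11.4.2 and Tables 12-13:

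- Count only events that began, or worsened, after the first dose.
- Show pre-dose events in a separate listing.
- Classify anything noted at the screening examination as pre-dose even if dispensing is on the same day. SAP section 6 makes the screening visit the treatment-initiation visit, so a bare comparison of start date with dispensing date would let same-day findings through.
- State how partial start dates are classified. The CRF's date instructions allow unknown parts for events that precede inclusion, which are the ones the filter has to catch.
- Say whether the total row counts patients or events.

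On the CRF screening page, direct pre-existing abnormal findings to Medical History. If the form is already in use, the SAP rule still works without this change.

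The cost is a short SAP paragraph and one line on the CRF; start and dispensing dates are already collected. The downside is lower headline AE percentages and one additional listing. It should be settled no later than the final SAP, before database lock.
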